8.4.2. Follow-up visits after EOT (Investigational arm only)

- Sputum AFB smear microscopy and MTB culture on liquid and solid media
- CXR

8.5. Details of Study Procedures

Standard-of-care testing for the treatment and differentiation of multi-drug resistant TB will be performed after obtaining informed consent form of the study. The following test results may be used for research purposes.

1) Medical history

Medical history, especially for TB treatment history, diabetes mellitus and abnormal color vision

2) Physical examination

Routine physical examination

3) Neurological examination

Neurological examination, especially for abnormal sensation on legs and feet.

Any neurologic AE is developed, information including location, severity, and the relationship to the

Confidential

MDR-END v14.0, 20Mar2020

study drug will be documented. Additional neurologic tests could be done, if necessary.

4) Sputum acid-fast bacilli (AFB) smear and culture

Approximately 4mL or more of sputum will be collected and mixed with the same amount of 4% sodium hydroxide and then centrifuged for 20 minutes at 3,000xg to get pellet for AFB smear microscopy and MTB culture. AFB smear will be performed with Auramine-Rhodamine fluorescent staining at first and then with Ziehl-Neelsen staining for positive samples. For MTB culture, tubes with samples in the solid media (Ogawa culture medium) and liquid media (BACTEC MGIT™ or other) are continuously incubated at 5~10% CO₂ incubator for 6 weeks.

5) Drug Susceptibility Test (DST)

Phenotypic DST will be performed at outside laboratories other than the treatment sites. Resistance to each drug tested is defined as $\geq 1\%$ bacterial growth in Löwenstein- Jensen medium using the absolute concentration method observed with the following critical concentrations of anti-tuberculosis drugs: isoniazid 0.2 $\mu\text{g}/\text{ml}$; streptomycin 10.0 $\mu\text{g}/\text{ml}$; ethambutol 2.0 $\mu\text{g}/\text{ml}$; rifampicin 40.0 $\mu\text{g}/\text{ml}$; para-aminosalicylic acid 1.0 $\mu\text{g}/\text{ml}$; prothionamide 40.0 $\mu\text{g}/\text{ml}$; cycloserine 30.0 $\mu\text{g}/\text{ml}$; kanamycin 40.0 $\mu\text{g}/\text{ml}$; capreomycin 40.0 $\mu\text{g}/\text{ml}$; ofloxacin 2.0 $\mu\text{g}/\text{ml}$; levofloxacin 2.0 $\mu\text{g}/\text{ml}$; and moxifloxacin 2.0 $\mu\text{g}/\text{ml}$. Pyrazinamide susceptibility is determined using the pyrazinamidase test.

Genotypic DST (MTBDRsl and etc.) could be performed, if available.

6) CXR

Plain chest PA is performed per routine diagnostic method at each site. If possible, below conditions will be followed: 120kV, tube current (in milliamperes) with automatic exposure control, and a 12:1 antiscatter grid with a 180-cm focus-detector distance.

7) HIV, HBV Test

Peripheral blood 5mL is collected in plain tube and ELISA performed to detect anti-HIV antibody, HBs Ag.

8) Complete Blood Count

Peripheral blood 3mL is collected in EDTA tube to test red blood cell count (RBC), mean corpuscular volume (MCV), white blood cell count (WBC) with differential count, hemoglobin, hematocrit, and platelet count.

9) Chemistry

Peripheral blood 3mL is collected in SST tube to test total bilirubin, albumin, alkaline phosphatase, AST, ALT, Creatinine, and electrolytes examination.

10) Urine HCG Test

Confidential

MDR-END v14.0, 20Mar2020

Urine 10-50mLs collected to test pregnancy by human chorionic gonadotropin (β -hCG) determination kit.

11) Color vision test

Identify number of plates accurately read using the Ishihara Test for Color Blindness (24 plates).

12) Electrocardiography

Measure QT interval.

8.6. Study Drug Adherence

- DOT (Directly Observed Therapy) is not performed per Korean guidelines for the treatment of tuberculosis.
- The study nurse checks the study drug adherence by comparing the drug packaging with residual pill count at each visit. In the event that a scheduled visit is changed, the administration status of the study drugs and other drugs during that period will be checked as well.

Drug adherence = (actually taken dosage/prescribed dosage) * 100

8.7. Withdrawal

- 1) When the investigator judges that participating in this clinical trial would not be in the best interests of the subject
- 2) When the subject withdraws consent
- 3) Treatment failure
- 4) When the subject becomes pregnant while on anti-TB medication.
- 5) When investigators get additional test results of resistance like below,
 - a) fluoroquinolone resistance (phenotypic or molecular method)
 - b) rifampicin monoresistance is confirmed
 - c) rifampicin susceptible

* Subjects who withdrawn from the study will receive the same treatment with other TB patients by standard of care treatment.

Confidential

MDR-END v14.0, 20Mar2020

9. Checking for Developing Resistance Against Study Drug

9.1. Subjects

When culture conversion fails 6 months into treatment among subjects assigned to the investigational group, identify whether resistance to linezolid and delamanid manifested in MTB isolate cultured in sputum or bronchoscopic specimens at the time of participating in the study and at 6 months after treatment.

9.2. Method

1) Linezolid resistance examination: Same as method in ① or ②.

① MGIT960: Judge resistance using 1.0 $\mu\text{g}/\text{ml}$ critical concentration.

② Broth microdilution method: Inoculate bacteria in Middlebrook 7H9 containing a suitable concentration of linezolid in culture media and determine minimal concentration for suppressing bacterial growth, and judge as having resistance when the minimal suppression concentration considerably increases than the strain when first participating in the research.

③ May check mutation of genes related to already known linezolid resistance.

2) Delamanid resistance test

① Agar proportion method using Middlebrook 7H11 culture media, and judged as having resistance when, for over 1% of control group, growth of strain is not included in drug at Delamanid 0.2 $\mu\text{g}/\text{ml}$.

② May check mutation of genes related to already known delamanid resistance.

10. Sample size justification and Statistical Analysis Method

10.1. Sample size justification

The hypothesis of this study is that the treatment success rate at 24 months after the initiation of treatment for MDR TB using the new regimen including new anti-TB drugs will not be inferior to conventional treatment regimens. (Non-inferiority test)

Presumptions when calculating sample size are as follows.

- 1) Level of significance, $\alpha = 0.025$ (one-sided test)
- 2) Type 2 error (β) set at 0.20 to maintain 80% for power of the test
- 3) Subject no. ratio (control arm : investigational arm) = 1 : 1
- 4) Primary outcome: treatment success rate at 24 months after the initiation of treatment
- 5) The hypothesis of the study is as follows.
 - ① Null hypothesis: Four drug regimen treatment success rates at 24 month are inferior to conventional treatment outcomes. ($H_0 : P_T - P_C \leq \delta$)
 - ② Alternative hypothesis: Four drug regimen treatment success rates at 24 month are not inferior to conventional treatment outcomes. ($H_1 : P_T - P_C > \delta$)

Based on the study result of Kwak et al, 'Changes in treatment outcomes of multidrug-resistant tuberculosis, Int J Tuberc Lung Dis 19(5):525-530'(3), presuming 24 month treatment success rate of control arm as 80% and 24 month treatment success rate of investigational arm as 90%, the non-inferiority margin (δ) is -0.10 which is regarded as non-inferior when the difference is less than 10% between the two arms. The number of study subjects is 48 per arm.

In addition, reflecting 1) proportion of fluoroquinolone-susceptible MDR-TB among participants with positive Xpert MTB/RIF assay of 50%, and 2) anticipating 5% lost to follow-up, the final number of participants is calculated as $N/(0.50*0.95)$ resulting in 102 persons per arm, 204 in total.

If a participant withdrew for any reasons within two weeks after enrollment, the participant will be replaced. Considering the number of replaced participants, the enrollment accrual ceiling is 220 persons maximum.

10.2. Statistical Analysis Method

1) Analysis Group Definition

Data obtained from subjects through clinical trials will be analyzed by mITT (Modified Intention-To-Treatment) analysis and PP (Per-Protocol) analysis. Efficacy evaluation will be based on a mITT (Modified Intention-To-Treatment) and additional analysis on PP (Per-Protocol) group. Safety analysis will be performed on the safety group.

- The mITT (Modified Intention-To-Treatment) group includes participants who are randomized after satisfying eligibility criteria and receive study drugs at least one time.
- The PP (Per-Protocol) group includes participants that satisfy the following among mITT group.
 - 1) When completing over 80% of the planned treatment (in other words, for control arm, 64 weeks or longer treatment; For investigational arm, 32 weeks or longer treatment in the 9-month treatment group and 42 weeks or longer treatment in the 12-month treatment group)
 - 2) Participants who completed the study per protocol during the clinical trial period.
- The Safety analysis group includes participants who receive study drugs at least one time.

2) Handling of Missing Data

When categorized as 'loss to follow-up', 'withdrawal', or 'withdrawal of consent', it is deemed as following.

- ① 'Treatment failure' in the case of dropping out due to 'loss to follow-up', 'investigator's decision', 'withdrawal of consent', 'treatment failure', or 'death' during the treatment
- ② 'Not accessible' in the case of dropping out due to pregnancy during the treatment
- ③ 'Treatment failure' in the case of dropping out due to 'relapse' after the treatment completion
- ④ 'Not accessible' when there is no evidence of treatment failure, such as bacteria reversion in the case of withdrawal due to 'loss to follow-up', 'investigator's decision', 'withdrawal of consent', 'pregnancy', or 'death' after the treatment completion

3) Basic Characteristics Analysis of Subjects Prior to Administration of Study Drugs

In order to check if there is any significant difference in demographic or clinical characteristics among the two arms prior to administration of study drugs, the serial data is summarized as mean, standard deviation, median and minimum and maximum, and the two arms are compared by independent t-test or Wilcoxon rank sum test. For categorical variables, the frequency and proportion per group is found and the two arms are compared by Chi-square test and Fisher's exact test. This analysis is carried out on the ITT analysis group.

4) Efficacy Evaluation

All statistical analysis of the two arms is carried out at significance level of 5% for both sides unless stated otherwise. For additional analysis, stratified analysis will be performed for primary and secondary outcome evaluation by stratification into sputum smear positive patient groups and sputum smear negative patient groups based on the sputum smear microscopy results.

① Primary Efficacy Evaluation

The primary outcome of this clinical trial is treatment success rate at 24 months after the initiation of treatment.

Describe the treatment success rate of the control arm and the investigational arm with a two-sided 95% confidence interval. Then, in order to test for non-inferiority of the investigational arm, when the lower limit of one-sided 97.5% confidence interval of the difference ($P_T - P_C$) between control and investigational arm is larger than the non-inferiority margin of -10%, it is concluded that the treatment success rate of the investigational arm is non-inferior to the treatment success rate of the control arm. The subjects whose treatment result is assessed 'Not accessible' are excluded from the primary outcome evaluation.

② Secondary Efficacy Evaluation

The secondary outcomes are analyzed as following and describe at exploratory levels.

- **Time to sputum culture conversion after the initiation of treatment (liquid and solid culture media)**

- In order to test whether the time to sputum culture conversion after the initiation of treatment of the control arm and investigational arm (liquid and solid culture media) are different statistically, the median time is estimated in each group using the Kaplan-Meier method, and the difference of the distribution of time to culture conversion of the two arms is compared using the Log-rank test.

- **Sputum culture conversion proportion at two months of treatment (liquid and solid culture media)**

- In order to test whether there is a statistical difference in sputum culture conversion proportion at two months of treatment between the control arm and the investigational arm (liquid and solid culture media), each arm is summarized by conversion frequency and proportion, and the sputum culture conversion proportions at two months between the two arms are compared using the Chi-square test and Fisher's exact test.

- **Sputum culture conversion proportion at six months of treatment (liquid and solid culture media)**

- In order to test whether there is a statistical difference in sputum culture conversion proportion at six months of treatment between the control arm and the investigational arm (liquid and solid culture media), each arm is summarized by conversion frequency and proportion, and the sputum culture conversion proportions at six months between the two arms are compared using the Chi-square test and Fisher's exact test.

Confidential

MDR-END v14.0, 20Mar2020

- **Proportion of treatment success at the end of treatment**

-Summarize the frequency and proportion of treatment success at the end of treatment in the investigational arm.

- **Proportion of relapse after treatment success**

-Summarize the frequency and proportion of relapse after treatment success in the investigational arm.

- **Proportion of deaths and time-to-death**

-Summarize the frequency and proportion of death in the investigational arm, and estimate median survival time using the Kaplan-Meier method.

- **Primary outcome evaluation between treatment groups according to pyrazinamide resistance**

-Presentation of treatment success rate in the control arm and the investigational arm in small groups according to the presence or absence of pyrazinamide resistance, and verification of non-inferiority of treatment success rate difference between the treatment groups

5) Safety Evaluation

Safety evaluation is performed using adverse events that occur during the clinical trial period. Summarize all adverse events and serious adverse events, adverse event frequency and percentage, and 95% confidence interval on it. Also, summarize and evaluate the occurrence rate of adverse events in relationship to the study drug and severity. The incidence of adverse events (CTCAE Grade 3 and above toxicity) between the two arms are compared using the Chi-square test or Fisher's exact test.

11. Safety Assessment

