3.1 General Principle of Result Analysis

Data obtained from subjects through clinical trial will be analyzed by mITT (modified Intention-To-Treatment) analysis and PP (Per-Protocol) analysis. Efficacy evaluation will be based on a mITT (modified Intention-To-Treatment) and additional analysis on PP (Per-Protocol) group. Safety analysis will be performed on mITT, PP and the safety group (study drug administration group).

Subject Group	Definition
mITT	
- The mITT group includes participants who are randomized after satisfying eligibility criteria and receive study drugs at least one time. The subjects are not confirmed to be additionally resistant to fluoroquinolone, mono-resistant to rifampicin, or susceptible to rifampicin.

PP	
The PP (Per-Protocol) group includes participants that satisfy the following among the mITT group.
 
When completing over 80% of the planned treatment
 
: For control arm, 64 weeks or longer treatment; For investigational arm, 32 weeks or longer treatment in the 9-month treatment group and 42 weeks or longer treatment in the 12-month treatment group

Safety	
Participants who completed the study per protocol during the clinical trial period
 
: More than 80% of the planned period before treatment is completed, the following cases are considered protocol violation and excluded from the analysis group
 
① withdrawal or death.② The sputum test before culture conversion was not conducted③ Administration of study drug in the control arm 
The Safety analysis group includes participants who have taken study drugs at least one time.
 
: Evaluation based on the administration of study drug (delamanid or linezolid)

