3.4 Demographic Characteristics and Characteristics Prior to Administration of Study Drug

As a way to check significant differences in demographic and clinical characteristics between the two arms prior to administration of study drugs, the serial data is summarized into mean, standard deviation, median, minimum, and maximum values, and the two arm are compared by an independent t-test or the Wilcoxon rank sum test. For categorical variables, the frequency and proportion per group is found and the two arms are compared by Chi-square test or Fisher's exact test. This analysis is performed for the ITT analysis group.

The following items will be evaluated for the subjects' characteristics prior to administration of the study drug and presented for each randomized arm.

Type	Endpoints
Enrollment of each site and randomization stratification factor	- To summarize the frequency and proportion of randomization per each site, stratification factor (presence/absence of cavitation on baseline chest radiographs, presence/absence of baseline diabetes mellitus)
Demographic characteristics and vitality signs	- Age, gender, height, weight, blood pressure, and pulse
Past history	- Past history of tuberculosis and the number of treatments - Diabetes mellitus, optic neuropathy, or peripheral neuropathy

	
 - Galactose intolerance, Lapp lactase deficiency, and glucose-galactose malabsorption - Other diseases
Medication history	
 - Other medication except for TB medication or use of prohibited medication while on study drug
Physical/neurological examination	
 - Physical examination result and neurological examination result
Drug susceptibility test	
 - Screening visit: Xpert MTB/RIF assay (MTB and RIF resistance), MTBDRsl (fluoroquinolone resistance and XDR-TB), resistance, and resistant drug - Baseline visit: Resistance and resistant drug
Sputum AFB smear and CXR (Chest CT)	
 - Sputum AFB panel (AFB smear, solid culture, liquid culture) - CXR (range of lesions and presence or absence of cavity), Chest CT (range of lesions and presence or absence of cavity)
HIV/HBV test	
 - HIV test and HBV test result

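### Protocol 10.2 and SAP 3.1 define the primary mITT set differently; the protocol's version keeps patients later found to be off-target, which dilutes the difference against a fixed 10-point margin

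*Combined protocol and SAP*

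**What the plan says.** Protocol 10.2, under the analysis group definitions, bases efficacy on an mITT set that "includes participants who are randomized after satisfying eligibility criteria and receive study drugs at least one time". SAP 3.1 repeats that sentence and adds a restriction: "The subjects are not confirmed to be additionally resistant to fluoroquinolone, mono-resistant to rifampicin, or susceptible to rifampicin". SAP 5 repeats the restriction, and SAP Table 1 lists the three resistance groups above the mITT count.

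Other sections bear on the same patients:

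- **Eligibility (Protocol 5.4 and 5.5).** Rifampicin resistance on a genotypic test is enough to enter, and only fluoroquinolone resistance already known at entry excludes. A patient whose later result shows one of the three patterns has therefore still met the criteria.
- **Withdrawal (Protocol 8.7, item 5).** These patients leave the study: "When investigators get additional test results of resistance like below", followed by the same three patterns.
- **Sample size (Protocol 10.1, repeated in SAP 2.3).** The target is inflated for a "proportion of fluoroquinolone-susceptible MDR-TB among participants with positive Xpert MTB/RIF assay of 50" per cent.
- **Missing data (Protocol 10.2 and SAP 3.2).** The rules assign failure or 'Not accessible' to named dropout reasons. Withdrawal for a resistance result is not one of them.
- **Baseline tables.** SAP 3.4 states: "This analysis is performed for the ITT analysis group". Protocol 10.2 assigns them to an ITT group too. Neither document defines that group.

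**The concern.** The primary analysis set has two definitions, and the patients on whom they differ could be numerous. The protocol's definition also conflicts with its own sample size, which counts only fluoroquinolone-susceptible MDR-TB, and with its stated purpose, which is limited to that disease.

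Patients withdrawn for an off-target result go on to standard care in either arm, so they carry little information about the randomised comparison. Keeping them with similar outcomes in both arms shrinks the observed difference in proportion to their share, while the margin stays at 10 points. In a non-inferiority trial that raises the chance of passing a regimen that is truly inferior by the full margin.

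Because no outcome rule names this withdrawal reason, a coding decision would settle both the denominator and the success count, in a trial where treatment is open-label.

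**Working it through.** **Inputs from Protocol 10.1:** one-sided alpha 0.025, power 80%, 1:1 allocation, control success 80%, investigational success 90%, margin −0.10, 48 evaluable per arm, factors 0.50 and 0.95, final size 102 per arm and 204 in total.

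**1. The plan's own figures.** With unpooled variance, n = (1.96 + 0.8416)² × (0.80×0.20 + 0.90×0.10) / (0.90 − 0.80 + 0.10)² = 7.849 × 0.25 / 0.04 = 49.06. The stated 48 is close, with power 79.1%. The inflation is 48 / (0.50 × 0.95) = 101.05, rounded up to 102 per arm, which matches. In reverse, 102 × 0.50 × 0.95 = 48.45. The size works only if the off-target half does not count, as in the SAP's set.

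**2. Formula for declaring non-inferiority.** P = Φ((pT − pC + 0.10)/SE − 1.96), with SE = √[(pC(1 − pC) + pT(1 − pT))/n].

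**3. Assumptions for the protocol's set.** 102 per arm, off-target share f equal in both arms, off-target patients scored as failures. This scoring is an assumption; the plan does not state it. On-target rates are then multiplied by (1 − f). The SAP's set has 102(1 − f) per arm at the on-target rates.

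Worked case, f = 0.50:
- On-target 80% v 70% becomes 40% v 35%. SE = √[(0.24 + 0.2275)/102] = 0.0677; (−0.05 + 0.10)/0.0677 − 1.96 = −1.22; P = 11.1% (exact binomial 11.0%). SAP's set, 51 per arm: 2.5% (exact 2.7%).
- On-target 80% v 90% becomes 40% v 45%. SE = √[(0.24 + 0.2475)/102] = 0.0691; (0.05 + 0.10)/0.0691 − 1.96 = 0.21; P = 58.3% (exact 59.0%). SAP's set: SE = √(0.25/51) = 0.0700; 0.20/0.0700 − 1.96 = 0.90; P = 81.5%.

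| Off-target share | False positive at 80% v 70%, protocol set | Same, SAP set | Power at 80% v 90%, protocol set | Same, SAP set (n per arm) |
|---|---|---|---|---|
| 10% | 3.5% | 2.5% | 89.6% | 97.0% (92) |
| 20% | 4.8% | 2.5% | 79.0% | 95.2% (82) |
| 30% | 6.3% | 2.5% | 69.8% | 92.1% (71) |
| 40% | 8.3% | 2.5% | 62.9% | 87.8% (61) |
| 50% | 11.1% | 2.5% | 58.3% | 81.5% (51) |

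**4. Where the direction changes (f = 0.50).** The chance of declaring non-inferiority, protocol set v SAP set, is 30.8% v 24.3% at on-target 80% v 80%, 36.0% v 33.9% at 80% v 82%, and 41.4% v 45.3% at 80% v 84%. The crossover lies between +2 and +4 points.

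**5. Dependence on the scoring (f = 0.50).** If off-target patients are kept with equal success of 50% to 80% in both arms, the false-positive rate at 80% v 70% is 11.1% to 13.5%, and power at 80% v 90% is 62.9% to 80.7%. The inflation comes from retention with similar outcomes, whatever the score. If all are coded 'Not accessible', they leave the primary evaluation and the two sets give the same primary result.

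**The case against.** The strongest reply is that the documents mostly point one way. The exclusion stands in SAP 3.1, SAP 5 and SAP Table 1; Protocol 8.7 withdraws these patients and Protocol 10.1 sizes the trial without them. SAP 1 says the plan exists to state the analyses clearly and prevent unplanned ones. This shows what was probably intended and weakens any suggestion that the set would be chosen after seeing the data. It is not a precedence clause, and Protocol 10.2 as worded still gives a different set.

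Three stronger readings are tempting, and the documents do not support them:

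- **That the protocol's set biases the test towards success.** This holds only below a true on-target advantage of roughly 2 to 4 points. At the advantage the sponsor plans for, it works against success.
- **That the two sets differ by half of those randomised.** The 50% is a planning figure for Xpert-positive participants. Known fluoroquinolone resistance is excluded before randomisation, genotypic testing may be done at screening, and withdrawals within two weeks are replaced, so the true share may be lower. Replacement alone cannot close the gap: the ceiling of 220 leaves 220 − 204 = 16 places, and cultures incubate for six weeks (Protocol 8.5).
- **That the plan scores these patients as failures.** Protocol 8.7 lists investigator judgement and resistance results as separate reasons, and the missing-data rules name only the former.

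A further objection is correct: copying the SAP wording unchanged would be unsafe. SAP Table 1 refers to resistance confirmed during the study, with no limit on specimen or time. Fluoroquinolone resistance acquired on treatment is a ground for treatment failed in Protocol 6.4, so that wording could remove genuine failures from the primary set.

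**Conclusion.** The contradiction stands and concerns the primary analysis set, so it should be corrected before outcomes are compared between the arms. Its effect, if the protocol's wording is followed and these patients are kept with similar outcomes in both arms, is dilution of the treatment difference. A regimen inferior by the full 10 points would pass too often, and one as good as the sponsor expects would pass less often.

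The size rests on 102 per arm, an equal off-target share in both arms, and failure scoring. Of these only the 102 is stated in the plan. The 50% share is the sponsor's assumption, and the lower rows of the range are as plausible from the text. The discrepancy would not affect the primary result if every such patient were coded 'Not accessible', but nothing in either document requires that coding.

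**What to change.** 1. Use one mITT definition in Protocol 10.2, SAP 3.1 and SAP 5. Exclude patients whose pre-treatment isolate shows fluoroquinolone resistance, rifampicin mono-resistance or rifampicin susceptibility, identically in both arms.
2. State that withdrawals under Protocol 8.7 item 5 based on the pre-treatment isolate are excluded from mITT and not scored as failures.
3. State that fluoroquinolone resistance acquired on treatment stays in mITT and is classified under the failure definition in Protocol 6.4. Reword the matching rows of SAP Table 1.
4. Add a sensitivity analysis of the primary outcome in all randomised and treated patients, with the outcome rule for off-target patients written down.
5. As a minor clean-up, replace the undefined ITT label for the baseline tables in Protocol 10.2 and SAP 3.4 with a named, defined set.

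The cost is wording in both documents and one extra analysis.
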